1.1 Demographic and clinical data

The prevalent CKD stage 3 – 5 population will be screened by the researcher. After verification of the in- and exclusion criteria, eligible patients will be invited to participate the HORUZ study, with approval of their treating nephrologist. After signing the informed consent, data at baseline and during followup visits will be collected on paper clinical report forms (Table 1). Hypertension is defined as an office BP \geq 140/90 mmHg or home BP \geq 130/80 mmHg, or current medication for hypertension.¹ Diabetes mellitus will be assumed to be present in patients who report use of insulin and/or oral hypoglycemic agents. CV diseases include coronary artery disease, as documented by coronary angiography or a history of myocardial infarction, congestive heart failure, cerebrovascular accident, or known peripheral vascular disease. Fluid assessments, including BIS measurements, will be recorded on the HORUZ registration form (Appendix).

The healthy controls included for the cross-sectional analysis will only be followed according to visit 0 and 1.

| | Baseline Visit 0 | Month 1 Visit 1 | Month 3 Visit 2 | Month 6 Visit 3 | Month 9 Visit 4 | Month 12/ end of study Visit 5 |
|--|---------------------|--------------------|--------------------|--------------------|--------------------|-----------------------------------|
| Consent | х | | | | | |
| Demographics: Age (y) Gender Height (cm) Smoking status Etiology CKD Hypertension Diabetes CV disease Tx list | x | | | | | |
| eGFR _{creat} | x | x | x | x | x | x |
| CrUrCl | | x | x | x | x | x |
| 24h urine | | x | x | x | x | x |

Table 1 Schedule of the main data to collect in CKD subjects.

| BP | x | | x | x | x | x |
|-----------------|---|---|---|---|---|---|
| ECG | x | | x | x | x | x |
| Echo cor | | x | | | | x |
| CV events | | x | x | x | x | x |
| Hospitalization | | x | x | x | x | x |
| Medication | x | | x | x | x | x |
| Whole body BIS | x | | x | x | x | x |
| Thoracic BIS | x | | x | x | x | x |
| SF36 | x | | | | | x |
| Adverse event | | x | x | x | x | x |

Abbreviations: BIS, bioimpedance spectroscopy; BP, blood pressure; CKD, chronic kidney failure; Creat, creatinine; CrUrCl, mixed creatinine

and urea clearance; CV, cardiovascular; ECG, electrocardiography; M, month; SF36, short form 36 questionnaire; Tx, transplantation.

1.2 Primary endpoint

The association between fluid status and kidney function decline in patients with CKD stage 3 (CKD-EPI 60-30ml/min), 4 (CKD-EPI 30-15ml/min) and 5 (CKD-EPI < 15 ml/min) is the primary objective of the HORUZ study.

The primary endpoint is the mean eGFR decline which will be compared between the FO-group and the non-FO-group. BIS-measured FO will be expressed as overhydration (OH) normalized to ECW and noted as a percentage of ECW (OH/ECW).^{6,44} FO is defined as an OH/ECW \geq 7% (or an absolute OH \geq 1.1 L).⁴⁵

Rate of kidney function decline will be assessed by the slope in eGFR_{creat} CKD-EPI (see formula below), defined as the regression coefficient between eGFR_{creat} and time, in units of mL/min/1.73m² per year. At least 3 eGFR_{creat} values are required to evaluate eGFR_{creat} slope. All eGFR_{creat} CKD-EPI will be uniformly calculated in the laboratory. eGFR_{creat} decline is assessed by changes in eGFR over time. Rapid eGFR_{creat} decline is defined as the quartile with the steepest eGFR slope (eGFR_{creat} decline > $3mL/min/1.73m^2$ per year).⁹

Investigating the Hemodynamic profile Of chronic Renal patients by Use of Bioimpedance HORUZ study

 $eGFR_{creat} = 141 \times min(S_{creat}/\kappa, 1)^{\alpha} \times max(S_{creat}/\kappa, 1)^{-1.209} \times 0.993^{Age} \times 1.018$ [if female] × 1.159 [if black]

 $\begin{array}{l} S_{creat} \left(standardized \ serum \ creatinine \right) = mg/dL \\ \kappa = 0.7 \ (females) \ or \ 0.9 \ (males) \\ \alpha = -0.329 \ (females) \ or \ -0.411 \ (males) \\ min = indicates \ the \ minimum \ of \ S_{creat}/\kappa \ or \ 1 \\ max = indicates \ the \ maximum \ of \ S_{creat}/\kappa \ or \ 1 \\ age = years \end{array}$

Average CrUrCl will be determined by creatinine and urea measurements in blood- and urine samples (Table 2).

Residual urine output (mL per 24h) will be collected every study visit and analyzed on volume, urea, creatinine, sodium, osmolarity and albumin/creatinine ratio (ACR) (Table 2).

Time to renal replacement therapy will be recorded.

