| Sponsor | The sponsor is the party that commissions the organization or performance of the research, for example a pharmaceutical company, academic hospital, scientific organization or investigator. A party that provides funding for a study, but does not commission it, is not regarded as the sponsor, but referred to as a subsidizing party. |
| SF36 | short form 36 questionnaire |
| SUSAR | suspected unexpected serious adverse reaction |
| TBW | total body water |
| Tx | transplantation |

SUMMARY

Rationale: Preservation of residual renal function is independently associated with reduced mortality and improved outcomes in patients with end stage renal disease. Fluid status and blood pressure influence the rate of kidney function decline early in the course of chronic kidney disease (CKD). The technique of bioimpedance spectroscopy (BIS) can offer valuable information on fluid dynamics and body composition, in addition to standard care.

Objectives: This study aims to investigate the role of thoracic and whole body BIS in the hemodynamic profile of patients with CKD. The primary objective is to associate the BIS-determined fluid status [fluid overload (FO) versus non-FO] with kidney function decline in patients with CKD stage 3 (CKD-EPI 59-30ml/min), 4 (CKD-EPI 29-15ml/min) and 5 (CKD-EPI < 15 ml/min). The secondary objective is to identify the clinical factors associated with FO during a longitudinal follow up. Secondary outcomes of interest are the central volume status (measured by echocardiography and thoracic BIS in combination with photoplethysmography), the cardiac systolic and diastolic function, CV events, hospitalizations, inflammatory- and nutrition status, and quality of life, between CKD stages 3, 4 and 5 and compare them to an age- and sex- matched healthy control group.

Study design: An non-randomized intervention study with a longitudinal follow up of the cohort and some cross-sectional analysis.

Study population: Prevalent CKD patients stage 3 - 5 not on dialysis and an age- and sex- matched healthy control group, will be included during a period of 18 months and prospectively followed up over a period of 12 months.

Intervention: During each study visit BIS- and blood pressure measurements will be performed, and blood- and urine samples will be taken in each subject.

Main study parameters/endpoints:

- Whole body fluid status, measured by whole body BIS

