Based on the above mentioned associations between risk factors and outcome in the CKD population, the question rises what specific hemodynamic profile (including FS and BP) is associated with a severe CV comorbidity cascade leading towards more CV events, hospitalizations, rapid decline of kidney function and acceleration of the initiation of renal replacement therapy.

Assessment of the hemodynamic profile, cardiac- and kidney function in predialysis patients

During progression to ESRD, accumulation of fluid occurs silently. Clinical assessment of FS is not straightforward in CKD patients. While prevalence of overhydration in CKD stages 3 - 5 is estimated at 50%,^{6,25,26} 20% of these patients is non-edematous at clinical examination.⁶ The gold standard to measure fluid distribution in the human body is dilution of deuterium and sodium bromide solution for extracellular water (ECW) and total body potassium for intracellular water (ICW). However, these techniques are invasive and not applicable in routine clinical practice. **Bioimpedance spectroscopy** (BIS) is a noninvasive and easy-to-use technology in fluid assessment. Some BIS instruments have been validated in hemodialysis patients against dilution methods.²⁷⁻³⁰ BIS provides the possibility to estimate total body water (TBW), extracellular volume (ECV), intracellular volume (ICV), fat-free mass, fat mass and muscle mass.^{31,32} Also, blood volumes can be accurately estimated by BIS and can optimize BP treatment.³³

In contrast to the hemodialysis population, the clinical use of BIS in fluid management of non-dialysis CKD stages 3 - 5 is less frequently implemented. Observational research has shown that BIS identifies FO in 20% of non-edematous patients with CKD stages 3 - 5, and showed impairment of body composition in absence of overt signs of malnutrition.^{6,25} BIS-derived parameters as FO or lean tissue mass are associated with more rapid decline in residual renal function (RRF), higher CV morbidity and mortality compared to euvolemic CKD-patients.^{9,10,26}

The combination of electrocardiography (ECG) and echocardiography is the easiest and cheapest reliable method to evaluate LVH. However, the gold standard is magnetic resonance imaging (MRI), this is not widely used because of individual MRI tolerance and costs.

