In order to investigate this hypothesis, we want to perform the HORUZ study. We are interested in the fluid status, BP and thoracic BIS signal of patients with CKD 3 - 5, not on dialysis. We aim to provide more evidence to further support the frequent use of BIS in diagnostic guidelines of patients with CKD.

OBJECTIVES

The primary objective of the HORUZ study is to associate fluid status with kidney function decline in patients with CKD stage 3 (CKD-EPI eGFR 60-30ml/min), 4 (30-15ml/min) and 5 (< 15 ml/min) and compare them to an age- and sex- matched healthy control group. Primary outcome is the mean eGFR decline which will be compared between the FO-group and the non-FO-group.

The secondary objective is to identify the clinical factors associated with FO during a longitudinal follow up. Secondary outcomes of interest are the central volume status (measured by echocardiography and thoracic BIS in combination with photoplethysmography), the cardiac systolic and diastolic function, CV events, hospitalizations, inflammatory- and nutrition status, and quality of life, between CKD stages 3, 4 and 5 and compare them to an age- and sex- matched healthy control group.

STUDY DESIGN

The HORUZ study is a non-randomized trial with intervention of regular BIS- and BP measurements, blood- and urine sampling. Prevalent patients with CKD stages 3, 4 and 5 and an age- and sex- matched healthy control group will be included. Inclusion period will last 18 months and CKD-patients will be followed up for 12 months.

STUDY POPULATION

1. Population

206 patients with CKD stages 3-5 will be included from the outpatient clinic of Ziekenhuis Zuid-Oost Limburg in Genk (Belgium).

A healthy control group for the cross-sectional part will be recruited through visitors and/or personnel of Ziekenhuis Oost-Limburg in Genk (Belgium).

2. Inclusion criteria

In order to be eligible to participate in this study, a subject must meet the following criteria:

- Prevalent non-dialysis patients with eGFR < 60 ml/min (for CKD subjects)
- Age > 18 years
- Signed informed consent

3. Exclusion criteria

A subject who meets any of the following criteria will be excluded from participation in this study:

- Acute kidney injury
- eGFR < 20ml/min directly post-nephrectomy
- Clinical conditions affecting BIS measurements: limb amputation, impaired skin integrity, brain stimulator, pacemaker with low threshold or unipolar pacemaker.

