- Clinical conditions affecting body composition: liver cirrhosis, active infectious disease or any acute CV event (defined as cerebrovascular event, myocard infarction, decompensatio cordis) during the 3 months before screening for inclusion
- Pregnancy

- Not able to sign informed consent

4. Sample size calculation

The primary outcome parameter is the mean eGFR decline which will be compared between the FOgroup and the non-FO-group. We hypothesize that the mean difference between eGFR between these two groups will be 2 μ mol/ml/year. Because the study of Levin et al. does not report a SD, we take the SD of the MDRD study¹: 4.7 μ mol/ml/year^{1,42,43}. In order to show an alpha of 0.05 and a power of 0.8, at least 86 patients would be needed per group. In order to correct for drop-outs, at least 103 patients per group have to be included.

METHODS

1. Study parameters/endpoints

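### Fluid overload is analysed only as present or absent, although OH/ECW is recorded as a percentage; a pre-specified continuous analysis should support the primary comparison.

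*Combined protocol and SAP*

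**What the plan says.** The Objectives section states the aim broadly: "The primary objective of the HORUZ study is to associate fluid status with kidney function decline". The Summary states it as a two-group question: "associate the BIS-determined fluid status [fluid overload (FO) versus non-FO] with kidney function decline".

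METHODS 1.2 (Primary endpoint) first puts the exposure on a continuous scale: "BIS-measured FO will be expressed as overhydration (OH) normalized to ECW and noted as a percentage of ECW (OH/ECW". It then calls a patient overloaded at an OH/ECW of 7% or more, or at an absolute OH of 1.1 L or more. The endpoint follows: "The primary endpoint is the mean eGFR decline which will be compared between the FO-group and the non-FO-group". Non-FO is whatever remains. It has no lower bound, and there is no under-hydrated category.

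The sample size section is built on the same contrast. It takes a difference of 2 per year, an SD of 4.7, alpha 0.05 and power 0.8, and concludes that "at least 86 patients would be needed per group", or 103 per group after allowing for drop-outs.

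The Statistical Analysis section names repeated-measures ANOVA and a chi-squared test between subgroups. Linear regression appears only in the sentence on secondary parameters, for baseline-corrected estimates. OH/ECW is nowhere named as a continuous predictor of eGFR slope.

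**The concern.** A two-group split treats a patient at 7.1% like one at 20%, and separates a patient at 6.9% from one at 7.1%. If decline changes gradually with fluid status, this discards information that the study has already collected: Table 1 schedules whole-body BIS at baseline and at visits 2 to 5, and the registration form records OH and ECW. The study is sized at about 80% power for the split, so lost precision matters.

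A second issue is the comparison group. The Introduction describes earlier work in which overload went with "higher CV morbidity and mortality compared to euvolemic CKD-patients". Here the non-FO group may also contain patients with negative OH, so the reference group is not necessarily euvolemic.

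**Working it through.** **Inputs.** From the sample size section: difference 2, SD 4.7, two-sided alpha 0.05 (sidedness is assumed; the text does not give it), 86 evaluable per group, so 172 in all. Power depends only on the ratio 2/4.7, so the unit printed there does not affect the result. From the Introduction: overhydration prevalence of about 50% in CKD stages 3 to 5, which puts the cut near the median. Assumed, because the documents give neither: the distribution of OH/ECW and the shape of its relation to decline. The 1.1 L alternative is ignored, and FO is treated as one cut on OH/ECW.

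**1. The plan's own figure.** n per group = 2 × [4.7 × (1.960 + 0.842)/2]² = 86.7, rounded up to 87, against 86 stated. It reproduces. With 86 per group the standard error is 4.7 × √(2/86) = 0.717 and the noncentrality is 2/0.717 = 2.79. Power is 79% from the noncentral t distribution (80% by the normal approximation).

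**2. Information kept by a split.** For a normal exposure and a linear relation, relative efficiency = φ(c)²/[p(1 − p)], where p is the FO share and c the cut in SD units.
- p = 0.5: 0.3989²/0.25 = 2/π = 0.637, a loss of 36.3%.
- p = 0.4: a loss of 37.8%.
- p = 0.3: a loss of 42.4%.

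**3. Power of a linear term in the same patients.** Under normality and a median cut, the two halves differ in mean exposure by 2 × 0.798 = 1.596 SD. A group difference of 2 therefore implies a slope of 2/1.596 = 1.253 per SD of OH/ECW. Residual variance = 22.09 − 1.253² × (1 − 0.637) = 21.52, SD 4.64. Noncentrality = 1.253 × √172/4.64 = 3.54.
- 1-df linear test: power 94%.
- 2-df test (linear term plus one spline term) with noncentrality 3.54² = 12.6: power 89%.
- The 1-df test reaches 80% with about 110 patients.

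**4. Other exposure distributions** (median split, linear relation, by simulation).

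| Distribution of OH/ECW | Information lost |
|---|---|
| Uniform or clearly bimodal | about 25% |
| Normal | about 36% |
| Gamma, shape 4 | about 41% |
| t with 5 df | about 46% |
| Log-normal, sigma 0.5 | about 48% |

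**5. Other shapes of relation** (simulated power; n = 172, normal exposure, 50% FO, group difference 2).

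| True shape | Split | Linear term | 3-knot spline, 2 df |
|---|---|---|---|
| Linear | 0.79 | 0.94 | 0.89 |
| Rising only above the cut | 0.78 | 0.93 | 0.95 |
| Step exactly at the cut | 0.80 | 0.60 | about 0.50 |

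**6. Unequal groups.** The FO share is not fixed by design. If 30% of 172 are FO (51.6 against 120.4), the standard error is 4.7 × √(1/51.6 + 1/120.4) = 0.782, and split power at the planned difference is about 72% by the normal approximation.

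**The case against.** The strongest reply is that the plan is coherent. The Summary defines fluid status as FO versus non-FO, the hypothesis concerns overload, and the endpoint and sample size use the same contrast. The cut is pre-specified from a cited source and is not chosen from the data. A threshold also suits a study that wants to support BIS in diagnostic guidelines. All of this stands. A reader of the Objectives section alone might infer that the primary analysis fails to match its objective; the Summary does not support that.

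A reader might also infer that the split always wastes more than a third of the information, or that a continuous test should replace the primary one. Neither follows. The loss varies with a distribution and a shape that the documents do not give. If 7% is a real threshold, the split is the better test, and replacing it would detach the primary test from its sample size. The 94% belongs to a linear term under exact linearity, not to the more cautious spline test.

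Finally, a reader might infer that under-hydrated patients in the non-FO group will hide a true association. That would need such patients to be numerous and to decline faster. The documents give neither their share nor their rate of decline. It would also need a U shape, which is incompatible with the linear relation behind the power gain.

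The objection does not remove the gap: no continuous analysis is planned, and the documents offer no evidence that decline steps at 7%.

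**Conclusion.** The point holds as a cheap improvement to the analysis plan. The sample size calculation is sound for the two-group test. Assuming a roughly normal OH/ECW, a linear relation and about 50% FO, the split costs about 36% of the information, or about 79% power against 94% (linear) or 89% (spline). Across the distributions tried at a median cut, the loss runs from about 25% to 48%. It is zero for a true step at the cut. Mixing of under-hydrated with euvolemic patients is possible but cannot be quantified from the documents.

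Because the better analysis depends on an unknown shape, the continuous model needs to be fixed before the data are seen. Added later, it would be exploratory.

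**What to change.** Keep FO versus non-FO as the primary comparison. In METHODS 1.2 and in the Statistical Analysis section, add one pre-specified key supportive analysis: a regression of per-patient eGFR slope on baseline OH/ECW as a continuous variable. Report the effect per 5 percentage points with its 95% confidence interval. Fit a 3-knot spline over the full range, including negative OH, to check the shape.

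The cost is a paragraph of text and one more model to report, with no new measurements. The linear term can mislead or lose power if the true relation is a step or U-shaped, which is why the spline is included and the FO contrast stays primary.

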2.3 Suspected unexpected serious adverse reactions (SUSAR)

Not applicable.

3. Follow-up of adverse events

AE according to the study are considered very unlikely, due to the fact that only non-invasive methods are used. All AEs will be followed until a stable situation has been reached and treated to standard procedures.

4. Data Safety Monitoring Board (DSMB)

Not applicable.

STATISTICAL ANALYSIS

A table with baseline characteristics of all subjects will be provided. Baseline characteristics of the population will be expressed as the mean \pm standard deviation if normally distributed, or as the median [25th – 75th percentile] as not normally distributed, for continuous and dichotomous data, and as the frequency (%) for categorical data. Measurements of drop-outs will be included until the moment of withdrawal from the study. Normality in distribution will be tested by the Shapiro-Wilk statistic. Repeated measurements ANOVA techniques will be used for analysis. Pearson's Chi-squared test will be used to assess whether there is any distinction between subgroups in rate of kidney function decline. In case the analysis of the baseline characteristics showed any clinically relevant imbalance, we will also perform a multivariable logistic regression analysis in order to correct for this imbalance. Differences in LVH will be corrected for systolic BP and haemoglobin, as these are predictors of LVH in predialysis population.¹⁵ Depending on the level of measurement a Chi-squared test or a T-test will be used to assess differences in secondary study parameters, and logistic and linear regression for baseline-corrected estimates. Tests will be considered significant if p-values are ≤ 0.05 .

ETHICAL CONSIDERATIONS

1. Regulation statement

The study will be conducted according to the principles of the Declaration of Helsinki (Fortaleza, Brasil, 2013).

2. Recruitment and consent

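### The primary outcome needs three eGFR values, so patients who start renal replacement therapy, die or leave early may have none; the plan does not reconcile this with its rule to keep drop-outs' data.

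*Combined protocol and SAP*

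**What the plan says.** - **Endpoint (METHODS 1.2).** "The primary endpoint is the mean eGFR decline which will be compared between the FO-group and the non-FO-group". The rate of decline is "defined as the regression coefficient between eGFR" and time, and at least three "values are required to evaluate eGFR" slope.
- **Rapid decline (METHODS 1.2).** It "is defined as the quartile with the steepest eGFR slope", so it also needs a slope.
- **RRT (METHODS 1.2).** "Time to renal replacement therapy will be recorded". No rule links RRT, or death, to the slope or to rapid decline. No rule says whether creatinine measured after RRT start may enter the slope.
- **Population (STUDY POPULATION 2 and 3).** Non-dialysis patients with eGFR below 60 are eligible. There is no general lower limit, because the cut-off of 20 applies only directly after nephrectomy. The objectives name stage 5.
- **Schedule.** Table 1 has eGFR at months 0, 1, 3, 6, 9 and 12. METHODS 3 describes research visits every 3 months after baseline, which would put the third value at month 6.
- **Withdrawal (METHODS 4 and 5).** An end-of-study visit repeats the visit 5 measurements, which include eGFR. After that there is no further follow-up and no replacement.
- **Analysis (STATISTICAL ANALYSIS).** "Measurements of drop-outs will be included until the moment of withdrawal from the study" and "Repeated measurements ANOVA techniques will be used for analysis".

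**The concern.** A patient with one or two eGFR values has neither a slope nor a rapid-decline status. Some of the ways to end up there, such as early RRT or early death, may be related to how fast the kidney is failing. Missing the outcome could then depend on the outcome itself. If that loss is also heavier in the FO group, the FO versus non-FO difference shrinks and the observed share of rapid decliners in FO falls. The drop-out allowance protects against a smaller sample, not against this.

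The drop-out rule does not settle the matter. One or two values can enter some repeated-measures analyses but cannot yield an individual slope, and the plan does not say which of the two is the primary analysis. Who counts in the main comparison is therefore left open.

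**Working it through.** **Plan's own figure.** STUDY POPULATION 4 gives a difference of 2 per year, SD 4.7, alpha 0.05 and power 0.80. I take these as slope units and the test as two-sided.

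n per group = 2 × 4.7² × (1.960 + 0.842)² / 2² = 86.7. The plan states 86, so the figure reproduces apart from rounding down. Two-sample t power is 86% at 103 per group and 79% at 86.

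**Allowed loss.** (103 − 86)/103 = 16.5%. Assume that it is spread evenly over 12 months. The share leaving too early to be scored is then:

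| Schedule | Exit visit attended? | Unscored if leaving before | Share |
|---|---|---|---|
| Table 1 | yes | month 1 | 16.5% × 1/12 = 1.4% (about 3 of 206) |
| Table 1 | no | month 3 | 16.5% × 3/12 = 4.1% (about 8 of 206) |
| 3-monthly | yes | month 3 | 4.1% |
| 3-monthly | no | month 6 | 16.5% × 6/12 = 8.3% (about 17 of 206) |

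In the rows with an exit visit, that visit supplies the third value for anyone who leaves after the second scheduled one. Early RRT and death come on top if the allowance does not already include them. Their rates are not in the documents.

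**Effect on the comparison (assumed model).**
- True slopes are normal with SD 4.7 and means −5 (FO) and −3 (non-FO). Only the difference of 2 and the SD come from the plan.
- The log-odds of being unscored rise by 1 to 3 per SD of steepness, with the same rule in both groups.
- The intercept is solved to give the stated overall share. The remaining means, SDs and group sizes (from 103 per group) go into a two-sample t power calculation.

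| Unscored overall | Unscored in FO / non-FO | Difference (true 2.0) | Power |
|---|---|---|---|
| 1.4% | 1.7–2.0% / 1.1–0.8% | 1.89–1.97 | 84–85% |
| 4% | 4.8–5.5% / 3.2–2.5% | 1.77–1.93 | 80–83% |
| 8% | 9.4–10.6% / 6.6–5.4% | 1.64–1.88 | 75–81% |

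With a coefficient of 0 (loss unrelated to slope) the difference stays at 2.0. Power is then 85% at 4% and 83% at 8%, from the smaller sample alone.

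**Second set of assumptions.** Here loss is fixed by group and all of it comes from the steepest pooled quartile.
- 2% lost in FO and 1% in non-FO: difference 1.96.
- 5% and 2%: 1.86.
- 10% and 5%: 1.78.
- 10% and 2%: 1.55, and the observed share of rapid decliners in FO falls from 31.7% to 24.1%.
- 5% in both groups: about 2.07, so equal loss does not shrink the difference.

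If only half of the loss comes from that quartile, the difference lies between 1.91 and 2.07 across these cases.

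**The case against.** Several stronger readings are tempting, and the documents do not support them.

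- **That the slope rule and the drop-out rule contradict each other.** Both can hold: a minimum for an individual slope, and retention of the available measurements in a repeated-measures analysis. They are unreconciled, not contradictory.
- **That a patient starting RRT in month 2 is necessarily absent.** The plan does not restrict the three values to those before RRT. If a month 3 or exit-visit creatinine counts, that patient has a slope, though a distorted one. The patient is absent only if post-RRT values are not used.
- **That the fastest decliners are the ones lost.** The hypothesis section links FO to faster decline. It says nothing about who is unscored, and early RRT may reflect a very low entry eGFR more than a steep slope.
- **That power falls to 75%.** This needs 8% unscored and the steepest coefficient. At 4% the power stays at the planned 80% or above.
- **That a random-slope model is already planned.** STATISTICAL ANALYSIS names only repeated-measures ANOVA, with no random effects and no FO-by-time term. In its classical form, that method may drop incomplete cases.

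The exit visit is the best defence, since it rescues most voluntary leavers after visit 1. It does not help after death or when it is missed. The slope it rescues is also weak: with values at months 0, 1 and 3 its standard error is 5.55 times the residual eGFR SD, against 1.14 times with all six visits (1/√Σ(t − t̄)², t in years). What stands is that patients with fewer than three values, RRT and death have no defined place in the primary comparison.

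**Conclusion.** The point holds as a weakness in the analysis rule. As written, a patient with one or two eGFR values has no primary outcome, and the plan does not reconcile that with keeping drop-outs' measurements.

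The size is probably small. If exit visits are attended on the Table 1 schedule, about 1.4% are unscored plus early RRT and death, and the loss of difference and power is minor. It becomes material towards 8%. These figures rest on even loss over time, on assumed slope means, and on an assumed link between steepness and being unscored. The direction towards zero requires that unscored patients are steeper and more often in the FO group, which is plausible given stage 5 enrolment but not shown. The change is still worth making because it is cheap and uses data already collected.

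**What to change.** 1. Make the primary FO comparison a linear mixed model with random intercept and slope and an FO-by-time term. Fit it to all eGFR values up to RRT start, death or withdrawal, and include patients with one or two values. Keep the three-value rule only for descriptive individual slopes.
2. Add a sensitivity analysis that ranks patients who start RRT without a slope as having the worst decline. It may label slow decliners with very low entry eGFR as rapid, which would inflate the FO association if FO is commoner in stage 5. It should therefore account for baseline eGFR or CKD stage, and it should not replace the main definition.
3. Report patients without a slope, RRT starts and deaths by FO group.
4. Reconcile Table 1 with the 3-monthly visits in METHODS 3, since they imply different times for the third value.

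The cost is a few sentences and slightly more analysis work. No new visits are needed, and the time to RRT is already recorded. The mixed model assumes that missingness is explained by the observed eGFR values, and a patient with a single value informs the intercept far more than the slope. That is why items 2 and 3 are needed alongside it.
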